11.2. Adverse Events of Special Interest

Adverse events of special interest will be selected using the standardized MedDRA Query (SMQ) search criteria or relevant grouped PTs for the combined Phase 1, Phase 2, and combined Phase 1/2 in the SAS.

The following TEAEs of special interest will be summarized:

1. QT prolongation:
 - a. Broad scope of SMQ Torsade de pointes/QT prolongation.

2. Differentiation syndrome:

The Differentiation Syndrome Review Committee (DSRC) will review and confirm selected cases. The analyses listed below will be summarized based on the cases generated by the DSRC.

- a. Incidence of the DS syndrome
- b. Time to first onset of DS syndrome
- c. Potential risk factors will be summarized by subjects with and without DS in the combined Phase 1/2. The potential risk factors are:
 - Age (<60, 60 - <75, ≥75 years)
 - Sex (Male vs Female)
 - Baseline ECOG (Grade 0, 1, 2)
 - IDH2 mutation (R172 vs R140)
 - Number of prior anti-cancer regimens (1, 2-5, >5)
 - Hemoglobin (<10, ≥10 g/dL)
 - Platelets (<10, ≥10 - < 40, ≥ 40 x10⁹/L)
 - WBC (<2, ≥2 - < 5, ≥5 - < 10, ≥10 - < 50, ≥ 50 x10⁹/L)
 - Bone Marrow Blast (<30%, ≥30-<50%, ≥50-<70%, ≥70%)
 - LDH (≤ULN, >ULN-<2 ULN, ≥2ULN)
 - Creatinine Clearance (≥ 60, ≥45 to < 60, ≥30 to <45 mL/min)
 - Cytogenetic risk (Intermediate vs Poor)
 - Prior Hydroxyurea use (None, Discontinued Prior to First Dose, Continued After First Dose)
 - Best Response (CR, Non-CR responder, Non-responder)
 - Time to Response (<2 cycles, ≥2-<4 cycles, ≥4 cycles)
3. Bilirubinemia:
 - a. Narrow scope of Biliary system related investigations, signs and symptoms SMQ

- b. Summary of Bilirubinemia SMQ by baseline UGT1A1 gene status will be presented in combined phase 1/2 R/R AML and overall subjects
4. Renal Failure:
 - a. Broad scope of Acute renal failure SMQ
5. Hepatic TEAE:
 - a. Broad or Narrow scope for all Sub-SMQs Drug related hepatic disorders - severe events only
6. Non-infectious Leukocytosis:
 - a. Defined as the occurrence of leukocytosis/WBC increase without concurrent infection and infestations or febrile neutropenia (within \pm 7 days).
 - b. Non-infectious leukocytosis will be summarized in combined Phase 1, Phase 2, and combined Phase 1/2.
 - c. Potential risk factors will be summarized by subjects with and without non-infectious leukocytosis in combined Phase 1/2. The potential risk factors are:
 - Age (<60, 60 - <75, \geq 75 years)
 - Sex (Male vs Female)
 - Baseline ECOG (Grade 0, 1, 2)
 - IDH2 mutation (R172 vs R140)
 - Number of prior anti-cancer regimens (1, 2-5, >5)
 - Hemoglobin (<10, \geq 10 g/dL)
 - Platelets (<10, \geq 10 - < 40, \geq 40 $\times 10^9/L$)
 - WBC (<2, \geq 2 - < 5, \geq 5 - < 10, \geq 10 - < 50, \geq 50 $\times 10^9/L$)
 - Bone Marrow Blast (<30%, \geq 30-<50%, \geq 50-<70%, \geq 70%)
 - LDH (\leq ULN, >ULN-<2 ULN, \geq 2ULN)
 - Creatinine Clearance (\geq 60, \geq 45 to < 60, \geq 30 to <45 mL/min)
 - Cytogenetic risk (Intermediate vs Poor)
 - Prior Hydroxyurea use (None, Discontinued Prior to First Dose, Continued After First Dose)
 - Best Response (CR, Non-CR responder, Non-responder)
 - Time to Response (<2 cycles, \geq 2-<4 cycles, \geq 4 cycles)

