### **9.8.3. Leukocytosis**

Initiation of treatment with the differentiating agents may lead to rapid WBC expansion not associated with infectious process and not manifesting with the signs and symptoms of IDH Differentiation Syndrome discussed above.

In subjects with elevated WBC, prompt initiation of hydroxyurea is suggested, as per standard local practices (eg, dose of 2 to 3 g PO twice or 3 times daily for  $WBC > 30 \times 10^9/L$ ). In case of severe leukocytosis ( $WBC > 100 \times 10^9/L$ ), use of leukapheresis may be appropriate. Subject should be regularly monitored for changes in WBC count and for new signs and symptoms of infection or IDH Differentiation Syndrome.

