10.3.2.4. Time to Response

Time to response will be assessed from the date of first dose to the date of first occurrence of response of CR, CRi, CRp, PR, or mCR/MLFS.

Time to response will be summarized using descriptive statistics in subjects who respond in the FAS for Phase 1 dose escalation, Part 1 Expansion, the combined Phase 1, Phase 2, and the combined Phase 1/2. Time to response will also be summarized by cycle. The time to response by IRAC will also be analyzed.

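### SAP 11.2 lists best response and time to response as potential risk factors for differentiation syndrome and leukocytosis, although both are on-treatment outcomes that can follow the event or be changed by it

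*SAP*

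**What the plan says.** SAP 11.2 sets up two tables with the same layout. For DS: "Potential risk factors will be summarized by subjects with and without DS in the combined Phase 1/2". For leukocytosis: "Potential risk factors will be summarized by subjects with and without non-infectious leukocytosis in combined Phase 1/2". Most of the listed factors are baseline quantities: age, sex, ECOG status, mutation type, prior regimens, blood counts, marrow blasts, LDH, creatinine clearance and cytogenetic risk. Each list then ends with two rows of another kind:

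- "Best Response (CR, Non-CR responder, Non-responder"
- "Time to Response (<2 cycles, ≥2-<4 cycles, ≥4 cycles"

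A third row, "Prior Hydroxyurea use (None, Discontinued Prior to First Dose, Continued After First Dose", is discussed under the objection.

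No landmark, time-dependent handling or rule that a factor must precede the event is given, and no test or model is planned. By contrast, the safety subgroup list in SAP 11.1 contains only variables fixed at baseline.

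**The concern.** A risk factor has to be known before the event it is meant to predict. Best response is settled only once a subject's response follow-up is complete, and time to response is known only when a response occurs. In a table of subjects who ever or never had the event, such rows mix three things: any real link between response and the event, the effect of the event on the chance of responding, and the longer observation of subjects who stay on drug.

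DS and leukocytosis are adverse events of special interest, each with management guidance in the protocol. A reader of a table headed as risk factors may conclude that responders, or early or late responders, are a group to watch, when the pattern may come only from the way the table is built.

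**Working it through.** The plan gives no event rate, sample size or test for these tables, so there is no figure to reproduce. The check has two parts.

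**1. What the documents say about order and exposure**

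- *Response can follow the event.* Protocol 10.8.3 describes clinical response arising after differentiation-like signs have appeared.
- *The event can prevent response.* Protocol Table 6 lets treatment be stopped at the investigator's discretion in clinically unstable subjects with such signs.
- *Responders can be observed for longer.* Under SAP 11.1 an event counts up to 28 days after the last dose. Protocol 7.1.4 continues treatment until progression or unacceptable toxicity.
- *Non-responders have no time to response.* SAP 10.3.2.4: "Time to response will be summarized using descriptive statistics in subjects who respond in the FAS". The three levels in SAP 11.2 have no place for them.

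The first and third points can push an association upward and the second downward.

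**2. Illustration under a true null**

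The DS hazard was made the same whether or not a subject responds, with 1,000,000 simulated subjects per scenario. None of these inputs comes from the documents:

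- mean time to stopping without response: 4 cycles (2.5 and 6 as variants);
- potential response time: 0.9 cycles plus an exponential with mean 4.5 cycles (2.5 and 8 as variants);
- mean further time on drug after response: 7 cycles;
- DS hazard per cycle: 0.05 for 5 cycles, 0.03 throughout, or 0.10 for 3.5 cycles;
- event window: to one cycle (28 days) after the last dose;
- probability that DS before response ends treatment: 0, 0.5 or 1.

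With no stopping for DS, the simulated response rate was 35% to 38%, near the 36.4% that the protocol reports for 44 subjects at 100 mg QD.

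Odds ratio (OR) = [p_R/(1 − p_R)] / [p_N/(1 − p_N)], where p_R and p_N are the proportions ever having DS among responders and non-responders. ORs come from unrounded proportions.

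| P(DS before response ends treatment) | DS hazard per cycle | p_R | p_N | OR |
|---|---|---|---|---|
| 0 | 0.05, 5 cycles | 0.212 | 0.131 | 1.79 |
| 0 | 0.03, throughout | 0.267 | 0.089 | 3.70 |
| 0 | 0.10, 3.5 cycles | 0.291 | 0.220 | 1.46 |
| 0.5 | 0.05, 5 cycles | 0.160 | 0.162 | 0.99 |
| 0.5 | 0.03, throughout | 0.233 | 0.112 | 2.40 |
| 0.5 | 0.10, 3.5 cycles | 0.210 | 0.265 | 0.74 |
| 1 | 0.05, 5 cycles | 0.101 | 0.191 | 0.47 |
| 1 | 0.03, throughout | 0.198 | 0.133 | 1.60 |
| 1 | 0.10, 3.5 cycles | 0.105 | 0.306 | 0.27 |

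The two variants of the time assumptions (hazard 0.05 for 5 cycles, no stopping) gave ORs of 2.20 and 1.51.

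Time to response behaves the same way. Across its three levels, from earliest to latest, DS occurred in 23%, 27% and 33% with the constant hazard and no stopping, but in 15%, 10% and 1% with the 5-cycle hazard and stopping after every DS before response. The gradient reverses although response has no effect on the DS hazard in either case.

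In the same runs, an unrelated baseline factor gave ORs of 0.99 to 1.01. A landmark at 2 cycles gave 0.97 to 1.03. It took subjects on treatment and event-free at that point and compared those with and without a response by then for DS in the next cycle.

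**The case against.** **The tables are only descriptive.** The factors are called potential, nothing is tested and no decision follows. That stands, and it limits the importance. It does not change what the heading of the table invites a reader to conclude.

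**Other summaries show the exposure difference.** SAP 9.1 summarises exposure by best response. SAP 11.1 gives adverse events by cycle, and selected ones by response period. SAP 11.2 item 2b gives time to first DS onset. These help a careful reader, but none of them puts event and response in order within the risk-factor tables or adjusts those tables for time on drug.

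**The link with response is worth showing.** Agreed. Given the mechanism set out in Protocol 10.8.3, setting response against these events is reasonable. The fault is that it appears under a risk-factor heading with no regard to timing, so the fix moves it and does not suppress it.

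**Stronger readings that the documents do not support.**

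- A reader might infer that the tables are bound to show response as a false risk factor, with a predictable OR. With a constant hazard h and exponential time on drug of mean m, the odds of the event are h × m, so the OR is the ratio of the mean durations: 8/3 = 2.67 or 10/3.5 = 2.86 for assumed means in months. That only returns the assumption. Adding the 28-day tail (w = 28/30.4 = 0.92 months) makes the odds (1 + hm)e^(hw) − 1. With h = 0.03 per month the ORs fall to about 2.3 (0.275/0.121) and 2.5 (0.336/0.136). The documents give neither durations by response nor a hazard, and this model leaves out the downward mechanism.
- A reader might infer that the hydroxyurea row is reverse causation, because Protocol 9.8.3 says "In subjects with elevated WBC, prompt initiation of hydroxyurea is suggested". But the row is headed as prior use, so both user levels began before the first dose, and a subject who first starts hydroxyurea for on-study leukocytosis does not belong in either. Protocol 8.3 also allows it before enrollment for leukocytosis, so the row partly marks baseline disease. What remains is an ambiguity: the last level could mean ongoing at first dose, or kept up later in response to later counts.

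**Conclusion.** The point holds for best response and time to response in both tables. They are on-treatment outcomes that depend on time on drug, can follow the event and can be altered by it, so these rows can show associations that are not risk factors. This rests on the wording of SAP 11.2 and on the protocol's own account of order, stopping and treatment duration; it does not depend on the simulation.

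Size and direction are unknown. The simulated null ORs of 0.27 to 3.70 show how far the result turns on unstated durations and hazards, and are not an estimate for this trial. The association may also cancel. Hydroxyurea is a wording clarification only. Importance is modest: these are descriptive safety tables, and the primary ORR analysis is untouched.

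**What to change.** 1. In SAP 11.2 items 2c and 6c, limit the lists to values known at first dose by removing Best Response and Time to Response.
2. Show response against event status in a separate table labelled as on-treatment association. Preferably, classify response at a landmark (for example C3D1) among subjects still on treatment and event-free, or treat response as a time-dependent covariate for time to first event.
3. As a minor clarification, define the hydroxyurea level for continued use as ongoing at first dose.

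The cost is SAP wording: two rows moved out of each list, one level defined, and one extra descriptive table. No new data are needed. Response dates are already required for time to response. DS onset is already to be summarised, and the ±7-day infection rule for leukocytosis already requires event dates. A landmark drops events that occur before it, so if most events are early the time-dependent form will retain more of them.

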11.3. Death

Cause of death will be summarized in the SAS with the following categories: on-treatment death, post-treatment death, and overall.

1. All deaths within 28 days of the last dose of study drug.
2. All deaths after 28 days of the last dose of study drug.
3. All deaths.

The 30-day and 60-day death rate will be summarized for all deaths. Death analysis will be summarized for the combined Phase 1, Phase 2 and the combined Phase 1/2 as described in items 3 to 5 of [Section 5.1](#).

A death listing will include deaths for all screened subjects during pre-treatment, on-treatment, and post-treatment periods.

11.4. Clinical Laboratory Evaluations

Descriptive statistics will be provided for clinical laboratory data at baseline, post baseline and changes from baseline. Graphical displays of select laboratory parameters over the course of the treatment will also be provided.

Clinical laboratory values will be graded according to NCI CTCAE version 4.03 for applicable tests. Shift tables of laboratory data from baseline to the worst CTC grade during treatment and from baseline to last value on treatment will be presented.

Unless otherwise specified, all laboratory tables in this section will be produced as described in items 1 to 5 in [Section 5.1](#) for the SAS.

A by-subject listing will be presented for each laboratory.

11.4.1. Hematology

For hematologic parameters, the change from baseline will be summarized by study visit.

For specific hematologic parameters (hemoglobin, platelet counts, ANC, WBC, and RBC), separate figures of hematological parameters change from baseline by investigator assessed and IRAC adjudicated best response in Phase 2 will be plotted for R/R AML subjects.

A shift table representing the shift from the baseline grade to the worst grade, separated by worst (high) and worst (low) assessments, will be provided by study visit for Lymphocytes, ANC, WBC counts, platelet counts, and hemoglobin.

A summary table of \geq Grade 1 worsening and \geq Grade 3 post baseline will be summarized for above hematology parameters in combined Phase 1/2 R/R AML and overall.

In addition, figures for the mean of hemoglobin, platelet counts, ANC and WBC by visit will be provided for the combined Phase 1, Phase 2 and the combined Phase 1/2.

11.4.2. Clinical Serum Chemistry

For serum chemistry parameters, the change from baseline will be summarized by study visit.

A shift table representing the shift from the baseline grade to the worst grade by study visit will be provided for each of these laboratory tests where CTC grades are available. Shift tables in maximum CTCAE grades of worst (high) and worst (low) assessments will be presented separately for each laboratory parameter.

A summary table of \geq one Grade worsening and post baseline \geq Grade 3 will be summarized for the chemistry parameters where CTC grades are available in combined Phase 1/2 R/R AML and overall. For total bilirubin, \geq one Grade worsening and post baseline \geq Grade 2 or post baseline \geq 2ULN will be summarized in overall and by month.

The proportion of subjects with clinically significant post-baseline change in hepatic and renal function will be summarized based on the criteria presented in the table below. The liver related parameters such as ALT, AST, total bilirubin, composite total bilirubin and ALT, and composite total bilirubin and AST will be summarized by UGT1A1 gene mutation status in combined Phase 1/2 R/R AML and overall.

Table 4: Serum Chemistry Changes of Interest

Chemistry Laboratory Test	Parameters for any value and the last value
ALT	ALT \geq 3ULN (presented as \geq 3- < \times 5 ULN, \geq 5- < \times 8 ULN and \geq 8ULN)
AST	AST \geq 3ULN (presented as \geq 3- < \times 5 ULN, \geq 5- < \times 8 ULN and \geq 8ULN)
Bilirubin Total	Bilirubin Total \geq \times 2ULN Bilirubin Total \geq \times 3ULN
Total Bilirubin and ALT	Composite of Total Bilirubin \geq \times 2ULN and ALT \geq \times 3ULN (ALT presented as \geq 3- < \times 5 ULN, \geq 5 < \times 8 ULN and \geq 8 ULN) concurrent and within 1 cycle of Total Bilirubin elevation and at any time after start of treatment
Total Bilirubin and AST	Composite of Total Bilirubin \geq \times 2ULN and AST \geq 3ULN, (AST presented as \geq 3 < \times 5 ULN, \geq 5 < \times 8 ULN and \geq 8 ULN) concurrent and within 1 cycle of Total Bilirubin elevation and at any time after start of treatment
Potassium	Hypokalemia < 3.0 mmol/L and >15% decrease from BL Hyperkalemia > 6.0 mmol/L and >15% increase from BL
Potassium and Uric acid	Composite of concurrent hyperkalemia (potassium >ULN and >25% increase from BL) and hyperuricemia (uric acid >ULN and >25% increase from BL)
Phosphorus and Uric acid	Composite of concurrent hyperphosphatemia (phosphorus >ULN and >25% increase from BL) and hyperuricemia (uric acid >ULN and >25% increase from BL)
Calcium and Uric acid	Composite of concurrent hypocalcemia (calcium <ULN and >25% decrease from BL) and hyperuricemia (Uric acid >ULN and >25% increase from BL)
Magnesium	Hypomagnesemia Grade \geq 2 and >25% decrease from BL

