7. Platelet count  $\geq 20,000/\mu\text{L}$  (transfusions to achieve this level are allowed). Subjects with a baseline platelet count of  $< 20,000/\mu\text{L}$  due to underlying malignancy are eligible with Medical Monitor approval.
8. Subjects must have adequate hepatic function as evidenced by:
  - Serum total bilirubin  $\leq 1.5 \times$  upper limit of normal (ULN), unless considered due to Gilbert’s disease, a gene mutation in UGT1A1, or leukemic organ involvement, following approval by the Medical Monitor;
  - AST, ALT and ALP  $\leq 3.0 \times$  ULN, unless considered due to leukemic organ involvement.
9. Subjects must have adequate renal function as evidenced by:
  - Serum creatinine  $\leq 2.0 \times$  ULN
  - OR
  - Creatinine clearance  $> 40$  mL/min based on the Cockcroft-Gault glomerular filtration rate (GFR) estimation:
$$(140 - \text{Age}) \times (\text{weight in kg}) \times (0.85 \text{ if female}) / 72 \times \text{serum creatinine}$$
10. Subjects must be recovered from any clinically relevant toxic effects of any prior surgery, radiotherapy, or other therapy intended for the treatment of cancer. (Subjects with residual Grade 1 toxicity, for example Grade 1 peripheral neuropathy or residual alopecia, are allowed with approval of the Medical Monitor.)

11. Female subjects of child-bearing potential must agree to undergo medically supervised pregnancy test prior to starting study drug. The first pregnancy test will be performed at screening (within 7 days prior to first study drug administration), and on the day of the first study drug administration and confirmed negative prior to dosing and Day 1 before dosing all subsequent cycles.

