### **9.8.6. Increased blood bilirubin**

AG-221 slows breakdown of bilirubin, causing blood bilirubin increased. Liver enzyme monitoring may be instituted. Elevated blood bilirubin may also cause skin yellowing.

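### SAP Table 4 reports joint bilirubin and transaminase elevation as post-baseline change but does not show who was already elevated at entry

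*SAP*

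**What the plan says.** SAP Section 11.4.2 describes Table 4 in terms of change: "The proportion of subjects with clinically significant post-baseline change in hepatic and renal function will be summarized". The two hepatic composites in that table pair total bilirubin at or above 2×ULN with ALT, or with AST, at or above 3×ULN. The qualifying condition on each is one of timing: "concurrent and within 1 cycle of Total Bilirubin elevation and at any time after start of treatment". Neither test carries a change-from-baseline condition.

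The other composites in Table 4 do carry one. For example: "Composite of concurrent hyperphosphatemia (phosphorus >ULN and >25% increase from BL) and hyperuricemia (uric acid >ULN and >25% increase from BL".

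Entry is governed by Protocol Section 8.2, inclusion criterion 8. ALT and AST may be up to and including 3.0×ULN, a cap that applies "unless considered due to leukemic organ involvement". Bilirubin may be up to 1.5×ULN, with exceptions for Gilbert's disease, "a gene mutation in UGT1A1, or leukemic organ involvement, following approval by the Medical Monitor". No upper limit is stated for any of these exceptions. On the drug itself, Protocol Section 9.8.6 says "AG-221 slows breakdown of bilirubin, causing blood bilirubin increased".

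Several splits of the composites are planned. SAP Section 11.4 sends laboratory tables to the Section 5.1 groupings (dose group, expansion arm, malignancy type). Table 4 adds three ALT/AST bands and separates any value from last value. The liver rows are also shown by genotype: "composite total bilirubin and AST will be summarized by UGT1A1 gene mutation status in combined Phase 1/2 R/R AML and overall". Baseline-referenced shift tables exist, but one test at a time: "Shift tables in maximum CTCAE grades of worst (high) and worst (low) assessments will be presented separately for each laboratory parameter".

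**The concern.** A proportion labelled as post-baseline change should count subjects whose liver tests changed. These two composites count subjects whose on-treatment values exceed fixed multiples of ULN, whatever the values were before the first dose. The entry criteria allow some subjects to start at or above those multiples, and the drug is expected to push one of the two tests upward.

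SAP Section 4.3 confirms that the study is single-arm, so no control group shows how often leukemia alone would produce the same picture. A reader of the summary table could not tell a joint elevation that arose on AG-221 from a bilirubin rise added to a transaminase elevation the subject brought into the study. If composite cases are few, one case of uncertain origin would be visible in the reported proportion.

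**Working it through.** The plan attaches no figure to this point, so there is none to reproduce. The check compares criteria, then works out how little a subject must change to be counted.

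**1. Composites within Table 4.** The three non-hepatic composites (potassium, phosphorus and calcium, each with uric acid) require a change of more than 25% from baseline on each test: 3 of 3. The hepatic composites have no such term: 0 of 2. The timing phrase fixes when a value must be seen, not whether it is new.

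**2. Entry limits against thresholds.** The ordinary bilirubin cap (1.5×ULN) lies below the 2×ULN threshold, so a qualifying bilirubin at baseline needs one of the exceptions. The ordinary ALT/AST cap (3.0×ULN, inclusive) touches the 3×ULN threshold, so exactly 3.0×ULN qualifies without any exception. Higher values qualify under the leukemic-involvement exception.

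**3. Change needed to be counted** = threshold ÷ baseline − 1. The baselines of 5×ULN for ALT/AST and 3×ULN for bilirubin are examples, not document figures.

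| Baseline status | Bilirubin | ALT or AST |
|---|---|---|
| Both below threshold | Must rise; from the 1.5×ULN cap, 2.0/1.5 − 1 = +33.3% | Must rise to 3×ULN |
| Only ALT/AST at or above | Must rise to 2×ULN | From 3.0: 3.0/3.0 − 1 = 0%. From 5: 3.0/5.0 − 1 = −40%, still counted |
| Only bilirubin at or above | From 3: 2.0/3.0 − 1 = −33.3%, still counted | Must rise to 3×ULN |
| Both at or above | 0% | 0% |

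In the second row, the bilirubin rise described in Protocol Section 9.8.6 is enough, provided ALT/AST stays at or above 3×ULN. In the last row nothing needs to rise. Protocol Section 10.6.4 schedules chemistry on Days 8, 15 and 22 of Cycle 1, so an entry elevation that lasts one week can be captured as an on-treatment value.

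**4. Whether a planned display separates these rows.** Dose, arm and malignancy type do not describe baseline liver tests. ALT/AST bands and any/last value describe on-treatment values. UGT1A1 genotype bears on bilirubin and does not identify raised ALT/AST at entry. Shift and grade-worsening tables give baseline status for each test singly, so they cannot show the joint baseline status of a composite case.

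**5. Illustrative ceiling for the second row.** Assumptions, none from the documents: 1% to 5% of subjects enter with ALT or AST at or above 3×ULN; 10% to 30% reach bilirubin at or above 2×ULN on drug; the two are independent; and every raised ALT/AST persists long enough to meet the timing condition.

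- Phase 2, 125 planned: 125 × 0.01 × 0.10 = 0.125; 125 × 0.05 × 0.30 = 1.875.
- Whole study, planned minimum 291: 291 × 0.01 × 0.10 = 0.291; 291 × 0.05 × 0.30 = 4.365.
- Weight of one case: 1/125 = 0.8 percentage points; 1/291 = 0.34 percentage points.

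If persistence is incomplete, these counts fall in proportion.

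**The case against.** The strongest reply is that fixed ULN multiples form a deliberately sensitive screen. Over-counting errs toward detecting harm, and the criteria are printed in full beside the counts, so nobody need rely on the word change. The contrast with the other composites is also weaker than 3 of 3 against 0 of 2 suggests. Those rows trigger at the bare limit of normal (the calcium component is likewise written against ULN), so they need a change term to screen out trivial excursions. The hepatic rows start at 2× and 3×ULN. For a subject below both thresholds at entry, both tests must rise to be counted.

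There is other cover too. Hepatic and bilirubin adverse events of special interest are summarized under SAP Section 11.2 and must begin or worsen on or after the start of study drug (Section 11.1). Protocol Section 15.11 requires repeat testing and a diagnostic work-up, including prior liver history, when ALT reaches 3×ULN. The Medical Monitor confirms every subject's eligibility before dosing (Protocol Section 8.4). Listings allow case-by-case tracing.

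Most of this stands. It is a sound reason not to add a change condition that would remove subjects from the count, and it keeps the point small. It does not close the gap: adverse-event tables depend on what is reported, shift tables treat one test at a time, and listings are not a summary.

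A reader might also infer that UGT1A1 genotype is the only planned split of the composites. The documents do not support that. Dose, arm, malignancy type, ALT/AST band and any/last value are planned as well, and the dose split gives some information on relation to drug. The narrower statement holds: none of these splits identifies subjects who entered with raised ALT/AST or bilirubin.

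**Conclusion.** The point holds as a minor one. The two hepatic composites are presented as post-baseline change, carry no baseline term, and are not displayed by baseline liver-test status. An eligible subject can be counted with flat or falling ALT/AST, and one admitted with both tests over threshold can be counted with no rise at all.

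The size is unknown. The documents do not say how many subjects entered at or above either threshold, and the number may be zero. The ranges of 0.1 to 1.9 in 125 and 0.3 to 4.4 in 291 are ceilings under assumed shares, independence and full persistence. They are not estimates, and they cover only the route through raised entry ALT/AST.

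A reader might go further and infer that the composite counts are materially inflated or that the liver safety assessment is unsound. Nothing in the documents shows either. The effect is confined to how one descriptive safety table is read. ORR and its 25% criterion are untouched.

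**What to change.** Keep every threshold count in Table 4. For the overall any-value count of each of the two composites, not crossed with the ALT/AST bands, add a split by baseline status using the baseline definition already in SAP Section 5.1:

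1. both tests below threshold (treatment-emergent);
2. only bilirubin at or above 2×ULN;
3. only the transaminase (ALT or AST, as the composite requires) at or above 3×ULN;
4. both at or above threshold;
5. baseline missing for either test.

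No subject leaves the count, so no signal can be lost. The data are already collected. The cost is 5 lines × 2 composites = 10 rows, most with small counts. Crossing them with the three bands and with any/last value would give 10 × 3 × 2 = 60 rows and is not worth doing. A flag for a rise of more than 25% from baseline, or relabelling the single-test ALT, AST and bilirubin rows as values, would be optional; shift tables already cover those single tests.

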### **9.8.5. Tumor Lysis Syndrome**

Tumor Lysis Syndrome can cause abnormalities in your blood such as higher than normal levels of potassium and phosphorus or low levels of calcium with elevation of uric acid levels (hyperuricaemia) and may affect kidney function. Monitoring electrolytes and kidney function is advised and subjects may need to be treated with additional fluids or other medications, as appropriate.

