- Data from all study centers will be combined in the analysis.
- P-values will be rounded to 4 decimal places. P-values that round to 0.0000 will be presented as '<0.0001' and p-values that round to 1.000 will be presented as '>0.9999.'
- Confidence intervals (CIs) will be presented as 2-sided 95% CIs unless otherwise specified.
- Summary statistics will consist of the number and percentage of subjects in each category for discrete variables, and the sample size, mean, median, SD, minimum, and maximum for continuous variables.
- All percentages will be rounded to one decimal place. The number and percentage of responses will be presented in the form 'xx (xx.x)', where the percentage is in the parentheses.
- All analyses and summary tables will have the analysis population sample size for each treatment group in the column heading (ie, number of subjects).
- The day of the first dose of the study drug will be defined as study Day 1.
- For all analyses, unless noted otherwise, baseline will be defined as the most recent non-missing measurement by the first administration of study treatment. For subjects who receive the single dose on Day -3, baseline will be defined as the most recent measurement by the dosing on Day -3. For subjects who do not receive the single dose on Day -3, baseline will be defined as the most recent non-missing measurement by the first dose date.
- To summarize efficacy/safety data by visit, the post-baseline results will be summarized by the scheduled visit as appropriate.
- Calculation of Cycles:
 - The start date of each cycle will be determined based on scheduled study visit date for each subject, except for Cycle 1 which will use the first dose date of study drug as starting day. Once the start dates, eg, $S_1, S_2, S_3 \dots$ are determined, the end date of each cycle is calculated as the one day before the start date of the following cycle, ie, $E_i = S_{i+1} - 1$. The cycle number for each date of interest, eg, AE or study medication will be calculated based on event start date and the cycle window start and end dates. If an event date is on or after S_i and before S_{i+1} , the corresponding cycle number will be i . For the last cycle, the end date will be the last dose date, unless otherwise specified.

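### SAP Table 4 sets the calcium limit for hypocalcemia at ULN instead of LLN, so a normal calcium can be counted as low when baseline calcium was well above normal

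*SAP*

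**What the plan says.** SAP 11.4.2 plans to tabulate the proportion of subjects with clinically significant post-baseline chemistry changes, using the criteria in Table 4. Three rows pair an electrolyte with uric acid:

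- Potassium: "Composite of concurrent hyperkalemia (potassium >ULN and >25% increase from BL".
- Phosphorus: "Composite of concurrent hyperphosphatemia (phosphorus >ULN and >25% increase from BL".
- Calcium: "Composite of concurrent hypocalcemia (calcium <ULN and >25% decrease from BL".

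The uric acid half is the same in all three: "hyperuricemia (uric acid >ULN and >25% increase from BL".

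Two other rows of the table define low values. Potassium uses "Hypokalemia < 3.0 mmol/L and >15% decrease from BL". Magnesium uses a CTCAE grade of at least 2 together with a fall of more than 25%.

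For baseline, SAP 5.1 states that "baseline will be defined as the most recent non-missing measurement by the first administration of study treatment". It does not have to be a normal value. Protocol 10.6.4 has chemistry done at local laboratories against their own ranges, and neither document gives a calcium range.

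**The concern.** A value below the upper limit of normal is not, for that reason, low. The calcium criterion therefore does not match its own label. The two companion composites use ULN properly, because they describe high values. The other low-direction rows use an absolute low cut-off or a grade. Calcium is the only low-direction row tied to ULN.

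The combination of abnormalities also matters. Protocol 9.8.5 describes tumor lysis syndrome as including "low levels of calcium with elevation of uric acid levels", and the row has that same pattern. Tumor lysis is not among the adverse events of special interest in SAP 11.2, so the uric acid composites in Table 4 are where the pattern would appear in the laboratory tables. In a row where counts are likely to be low, a single subject whose high calcium returned to normal could be shown as hypocalcemic.

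**Working it through.** The plan states no figure for this row, so there is nothing to reproduce. The check is of the rule's logic.

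**The rule as an inequality.** Let B be baseline calcium and C the post-baseline value. A fall of more than 25% means C < 0.75 × B.

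- Written rule: C < ULN and C < 0.75 × B, that is, C < min(ULN, 0.75 × B).
- LLN rule: C < min(LLN, 0.75 × B).

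The two rules differ only for values with LLN ≤ C < min(ULN, 0.75 × B). Such values exist only if 0.75 × B > LLN, that is, B > LLN/0.75. At or below that baseline both rules reduce to C < 0.75 × B and agree exactly.

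The ULN condition removes a value only if C can fall by more than 25% and still be at or above ULN. That requires B > ULN/0.75. Between LLN/0.75 and ULN/0.75, the 25% fall alone decides.

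**Numbers.** The reference ranges below are assumptions.

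| Assumed range | LLN/0.75 | as multiple of ULN | 0.75 × ULN | ULN/0.75 |
|---|---|---|---|---|
| 2.10–2.60 mmol/L | 2.80 | 1.08 | 1.95 | 3.47 |
| 2.20–2.60 mmol/L | 2.93 | 1.13 | 1.95 | 3.47 |
| 8.4–10.2 mg/dL | 11.20 | 1.10 | 7.65 | 13.60 |
| 8.5–10.5 mg/dL | 11.33 | 1.08 | 7.88 | 14.00 |
| 8.6–10.3 mg/dL | 11.47 | 1.11 | 7.73 | 13.73 |
| 9.0–10.5 mg/dL | 12.00 | 1.14 | 7.88 | 14.00 |

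In every range 0.75 × ULN is below LLN. A subject whose baseline is at or below ULN must therefore already be truly low to meet the 25% fall, and the choice of limit makes no difference for that subject.

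**Examples, assuming 8.5–10.5 mg/dL** (calcium part only; uric acid must also qualify concurrently):

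| Baseline → post | Fall | Post value | Written rule | LLN rule |
|---|---|---|---|---|
| 9.5 → 7.0 | 26.3% | low | yes | yes |
| 10.5 → 8.5 | 19.0% | normal | no | no |
| 11.0 → 8.5 | 22.7% | normal | no | no |
| 11.5 → 8.6 | 25.2% | normal | yes | no |
| 12.5 → 9.2 | 26.4% | normal | yes | no |
| 14.0 → 10.4 | 25.7% | normal | yes | no |

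**Does anything else close the gap?** The eligibility criteria in Protocol 8.2 and 8.3 set no calcium limit, and nothing in either document redefines the bound in this row.

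**The case against.** The strongest reply is that the slip hardly matters, and most of that reply stands. The 25% condition confines the error to subjects who start well above ULN, and those subjects must also meet both uric acid conditions at the same time. SAP 11.4 and 11.4.2 separately plan CTCAE shift tables with high and low directions shown apart, tables of grade worsening, and by-subject listings. A spurious count could be checked against these. Reported tumor lysis events would appear among the adverse events. The SAP never says that this row measures tumor lysis; it introduces the table as concerning hepatic and renal function. The link to Protocol 9.8.5 is an inference from the matching pattern.

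Some stronger readings are tempting and do not hold:

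- *Any normal calcium counts as hypocalcemia.* The 25% fall prevents this unless baseline exceeds LLN/0.75.
- *Any high calcium that normalizes while uric acid rises is counted.* A fall from 2.75 to 2.50 mmol/L is only 9.1% and does not qualify. Uric acid must also be above ULN and up by more than 25%.
- *The ULN limit does nothing.* It excludes values when baseline exceeds ULN/0.75.

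What the reply does not remove is that the stated criterion contradicts its label. A programmer must either code it literally or depart from the SAP, and Protocol 12.6 commits the sponsor to reporting deviations from the planned analysis.

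**Conclusion.** The calcium criterion is wrong as written, and the consequence is minor. It can label a normal calcium as hypocalcemia only in subjects whose baseline exceeds LLN/0.75, about 2.80 to 2.93 mmol/L (11.2 to 12.0 mg/dL), and only when the 25% fall and both uric acid conditions are also met.

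The algebra needs no outside figure. The numerical thresholds rest on the assumed reference ranges, since actual limits are laboratory-specific. The documents give no distribution of baseline calcium, so no count of affected subjects can be derived; it may be zero.

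A reader might infer that tumor lysis reporting as a whole is unreliable. The documents do not support that: one descriptive row is affected, and calcium is also graded and listed elsewhere. The primary endpoint, sample size and decision rule are untouched.

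**What to change.** In SAP Table 4, Calcium and Uric acid row, replace ULN with LLN for calcium. Leave the 25% fall and the uric acid conditions as they are. Before amending, confirm against the signed SAP that the row does read ULN.

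The cost is one word in the SAP and one line of code. No true low value is lost: any calcium below LLN is also below ULN, so the corrected rule selects a subset of what the written rule selects and drops only values that are not below LLN. If tables have already been produced from the written rule, rerun this one row and note the correction in the clinical study report.
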